### **Benefit risk assessment**

The parameters measured in the context of the endometrial, adrenal and skin safety monitoring have been aligned with clinical experts and represent a positive benefit risk balance between their ability to detect relevant pathologies and the low procedure related risks associated with them.

These safety measures for subjects participating in the vilaprisan studies intend to ensure that potential tumors or diseases of the uterus, the skin or the adrenal glands are detected. If detected, it is important to understand that these tumors or diseases are not automatically related to the study drug as they can occur in a certain number of women independently of participation in a clinical study and independently of whether vilaprisan was taken as a study drug or not (“background incidence”). These measures can help to detect such findings,

probably even at an earlier stage than it would have become apparent otherwise. Furthermore, the safety measures will generate important data allowing to examine whether vilaprisan has a role in the development of such tumors and diseases.

The safety of short-term treatment with vilaprisan is supported by the available pre-clinical and clinical data. Therefore, it is Bayer's assessment that no acute or long-term risk is expected for the subjects who have been treated in any of the clinical studies performed with vilaprisan.

With regards to efficacy vilaprisan has demonstrated in Phase 1 a dose-dependent ovulation inhibition and induction of amenorrhea in healthy women. Two Phase 2 studies (15788 – ASTEROID 1 and 17541 – ASTEROID 2) with a treatment duration of up to 24 weeks were conducted in women with uterine fibroids. The results of both studies demonstrated a clinically meaningful reduction of symptoms associated with uterine fibroids, especially of HMB, improvements of subjects' health-related quality of life (HRQoL) and a reduction of fibroid size.

#### **4. Study objectives**

The primary objective of this study is to show superiority in treatment of HMB of vilaprisan in subjects with uterine fibroids compared to placebo.

The secondary objectives of this study are to additionally evaluate the efficacy and safety of vilaprisan in subjects with uterine fibroids. With the implementation of protocol amendment 5, Version 5.0, additional focus was put on safety evaluations of the endometrium, adrenal glands and skin.

The other objectives of this study are to evaluate the variability in exposure in relation to the efficacy and safety for vilaprisan and to collect patient-reported outcome (PRO) and clinician-reported outcome (ClinRO) data.

#### **5. Study design**

*This section was changed in Amendment 1, see Section 15.1.1*

This is a randomized, parallel-group, double-blind, placebo-controlled, multicenter study.

The study is conducted in the US, Japan and European countries.

Overview of the study design before the temporary pause is shown in [Figure 5–1](#).

With the implementation of the protocol amendment 5, Version 5.0, this study design is no longer valid. No subjects will receive further study drug.

**Figure 5–1: Design overview - amended**

Treatment Group A1	Screening up to 120 days	Randomization	Vilaprisan 2 mg 12 weeks	Bleeding episode	Vilaprisan 2 mg 12 weeks	Follow-up Day 7 to 15 of the 2nd menstrual cycle after EoT
Treatment Group B1	Screening up to 120 days	Randomization	Placebo 12 weeks	Bleeding episode	Vilaprisan 2 mg 12 weeks	Follow-up Day 7 to 15 of the 2nd menstrual cycle after EoT
Treatment Group B2	Screening up to 120 days	Randomization	Vilaprisan 2 mg 12 weeks	Bleeding episode	Placebo 12 weeks	Follow-up Day 7 to 15 of the 2nd menstrual cycle after EoT

EoT = end of treatment

During the screening period, subjects had to demonstrate eligibility including the presence of at least 1 uterine fibroid  $\geq 30$  mm and  $< 120$  mm in largest diameter based on ultrasound, HMB in at least 2 bleeding periods, each with menstrual blood loss (MBL)  $> 80.00$  mL documented by the alkaline hematin (AH) method, and endometrial biopsy results without significant histological disorder.

Eligible subjects were randomized in 1:1:1 ratio to one of the three treatment groups (Group A1, B1, or B2) and stratified by country/region (US, Japan and other countries). Treatment was started as described in Section 7.1.

After the end of the final treatment period, subjects were planned to be followed up for until day 7 to 15 of the 2nd menstrual cycle after end of treatment visit.

The **primary efficacy** variable is:

- Amenorrhea (yes/no), defined as MBL  $< 2$  mL during the last 28 days of treatment.

**For secondary variables**, see Section 10.3.1.2 and 10.3.2.2.

### Justification of the design

#### Placebo control and blinding:

A double-blind placebo-controlled design was considered necessary to differentiate drug effects from the natural course of disease and background findings. To minimize subject burden due to randomization to placebo treatment, all subjects were planned to receive active treatment during a part of the study.

#### Study design valid with the implementation of the protocol amendment 5, Version 5.0:

The study was temporarily paused since December 2018. No further subjects will be recruited and none of the enrolled subjects will receive further study drug treatment. All subjects who were randomized and started treatment before the temporary pause will be asked to have a comprehensive safety evaluation (with particular focus on endometrial, adrenal and skin safety) performed. This also applies to subjects who have completed or discontinued the study

before or during the temporary pause, provided they have taken at least one dose of study medication.

### **Efficacy / pharmacodynamic assessments:**

Menstrual bleeding and the impact uterine fibroids symptoms have on the subjects' daily life are determined as efficacy parameters.

Fibroid size, uterus size (by ultrasound), endocrine hormone levels, and bleeding are determined as pharmacodynamic (PD) parameters.

### **Safety monitoring:**

Safety parameters are regularly and closely monitored throughout the study (eg, questioning for AEs, measurement of laboratory values, close observation of subjects in case of increased liver parameters, a separate liver symptom questionnaire, i.e. the liver symptom inquiry, vital signs, endometrial thickness, abnormal menstrual bleeding, and size of follicle like structures comprising follicles and functional ovarian cysts). A comprehensive screening program for adrenal tumors and a skin examination by a dermatology expert are implemented with the protocol amendment 5, Version 5.0.

### **Endometrial monitoring**

A careful endometrial safety monitoring assessment was applied in this study from the beginning, including regular ultrasound investigations during the treatment period, observation of bleeding patterns, and endometrial biopsies at defined time points. Clear decision trees were outlined as to when to perform an additional unscheduled endometrial biopsy in case of endometrial thickening and/or on the clinical management of endometrial thickening/HMB/abnormal menstrual bleeding pattern (see Section 9.7.2). Highly reliable diagnosis of any findings in the endometrial biopsies is ensured through the involvement of a panel of highly experienced and well renowned expert pathologists who will assess every biopsy sample taken from study participants.

With the protocol amendment 5, Version 5.0, additional requirements for endometrial safety screening are outlined for subjects who took at least one dose of study medication, see Section 9.6.3.2.

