##### **Multi-reader assessment**

The multi-reader assessment will be performed by a panel of pathologists who will be blinded regarding treatment group and time point of sample.

A majority consensus diagnosis of the multi-reader assessment is derived from the individual diagnoses of the pathologist panel (single-reader diagnoses), according to pre-specified rules. In the absence of a majority consensus, the most severe diagnosis is used. The derived diagnosis resulting from these rules will be used for primary analysis of endometrial biopsy data. The individual diagnoses of each reader will be captured in addition.

Starting with the protocol amendment 5, Version 5.0 the majority diagnosis of the multi-reader assessment including the single reader assessments (Part II of the evaluation form, i.e. the diagnoses benign endometrium, endometrial hyperplasia or malignant neoplasm) will be communicated to the study sites once the majority consensus diagnosis is available.

A repeat endometrial biopsy will be requested, if sample is inadequate for evaluation in the majority multi-reader assessment.

For follow-up of biopsies with abnormalities see Section [9.6.3.2.5](#).

Besides standard safety criteria (e.g., proliferative/secretory/atrophic endometrium, endometrial hyperplasia, malignant neoplasm) the pathologists will document the presence of PAEC (see Section [9.6.3.2.6](#)). The results of the PAEC assessment are not reported back to the investigators except if in the last biopsy within the study, PAEC is still present and further biopsy sampling is needed.

The main study evaluation will be based on the majority diagnosis of the multi-reader assessment. An analysis of single-reader diagnoses that is more severe than the majority diagnosis will be provided in the Study Report.

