#### **9.6.3.2.5 Follow-up of endometrial biopsies with abnormalities**

Endometrial biopsies with a safety-reader diagnosis (Part II of the evaluation form) other than “benign endometrium” (i.e. “Malignant neoplasm”, “Endometrial Hyperplasia” with or without atypia) should undergo an expedited multi-reader assessment. If an expedited multi-reader assessment is not possible (e.g. due to sample export regulations), follow-up procedures will be decided based on the safety-reader diagnosis.

Endometrial biopsies with a multi-reader majority diagnosis (Part II of the evaluation form) other than “benign endometrium” (i.e. “Malignant neoplasm”, “Endometrial Hyperplasia” with or without atypia) should be followed-up according to investigator assessment, i.e., either by performing endometrial biopsies, until resolution (i.e. until a follow-up biopsy shows a majority diagnosis of “Benign endometrium”) and/or by performing a therapeutic intervention as per local standard of care.

The timing of follow-up biopsies and/or possible therapeutic interventions according to local standard of care will be determined by the investigator (or by a gynecologist in case the investigator or sub-investigator is not specifically trained in gynecology) according to the observed abnormality. Typically, at least one endometrial shedding should have occurred before a follow-up biopsy is performed.

The follow-up biopsies should be performed within the study framework and analyzed by blinded multi-reader assessment. In case follow-up biopsies and/or other interventions are conducted at non-study sites, all efforts should be taken that results are obtained and documented appropriately.

For FUP of a majority diagnosis of “Benign endometrium – PAEC yes” please see Section [9.6.3.2.6](#).

For reporting of abnormal biopsy results as adverse event of special interest or SAE, please see Sections [9.6.1.1](#) and [9.6.1.6](#).

---

 or by a gynecologist in case the investigator or sub-investigator is not specifically trained in gynecology.

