### **9.6.3.2.6 Follow-up of PAEC**

Besides standard criteria (i.e., proliferative/secretory/atrophic endometrium, endometrial hyperplasia) presence of PAEC will be analyzed in all endometrial biopsy samples as part of the multi-reader assessment. The diagnosis of PAEC is based on a constellation of histologic features that, taken together, are characteristic. None of the features is unique, and to some extent any may be seen in subjects who have not been treated with PRMs. The common histologic features are endometrial glands showing cystic dilatation and an irregular architecture lined by inactive gland cells and compact, nondecidualized stroma.

If PAECs have been detected in the biopsy at the last visit before leaving the study according to the majority diagnosis resulting from the multi-reader assessment, the site will be informed and an additional biopsy should be scheduled. In case PAEC findings are still present, the study site will be informed and an additional biopsy is to be taken to evaluate resolution, with the timepoint of this additional biopsy to be determined case-by-case. If needed, more than one repeated biopsy may be taken and analyzed, except for cases with PAEC already present in the pre-treatment biopsy.

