6.4.1 Secondary safety variables

6.4.1.1 Endometrial histology

For endometrial histology evaluations (e.g., benign endometrium, presence or absence of hyperplasia or malignancy) the following time intervals / time points will be considered:

• Any time point

- Intervals A (acc to Figure 4–1)
- Intervals B (acc to Figure 4–1)
- "Exit examination" intervals
- Bleeding episode after last treatment period time windows in subjects with at least 56 days of treatment within the treatment period (by TP1, TP2 and overall):
 - From start of the patients' last treatment period until Day 55 of the same treatment period
 - From Day 56 of the same treatment period until the last day of the 1st bleeding episode after the treatment period
 - After 1st bleeding episode of the same treatment period, i.e., from 1st day after the end of the 1st bleeding episode to the last day of the 2nd bleeding episode
 - After 2nd bleeding episode of the same treatment period, i.e., from 1st day after the end of the 2nd bleeding episode to the last day of the 3rd bleeding episode
 - After 3rd bleeding episode of the same treatment period, i.e., from 1st day after the end of the 3rd bleeding episode to the last day of the 4th bleeding episode

Analyses will present the number and percentage of either subjects or biopsies. A subgroup analysis by exposure group (i.e., treatment duration \leq 90 days, 91 to 180 days, etc.) will be presented for endometrial biopsy main results.

Presentations will be done for

- the Safety read (Reader #1 or #5)
- the Majority read (Reader #2 #4)
- All reads (Reader #1 #5)

Safety read: For the safety read only one result will be available per biopsy (based on either Reader #1 or #5), whereas for the "majority read" and "all reads" more than one reader result needs to be considered.

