Majority read: Majority read results will only be provided in case biopsy data from Readers #2, #3 and #4 are available. Majority read will be determined for main results and subcategories (see Table 6–1). First, adequacy (for part II and III) or sufficiency (for part IV) of tissue will be investigated by all readers. If at least 2 of the 3 readers consider the tissue adequate/sufficient, the majority for the main results will be assessed. If there is a majority with respect to the main result, majority of the respective subcategories will be determined. If no majority result is available (3 different results in 3 readers, 2 different results in 2 readers), either "no consensus" or the worst case will be presented. Table 6–1 presents an overview of the biopsy results including the approach which is used in case no majority is available.

For subcategories where multiple selections are possible, an individual feature will be considered a majority read result if at least 2 readers have ticked this feature. That means that more than just one subcategory can be a majority read result for a biopsy.

All read: All read results will be based on all biopsies with results from at least one reader. A biopsy is considered non-benign in case "Benign endometrium" = "No" or "Endometrial Hyperplasia (WHO 2014)" or "Endometrial Hyperplasia (WHO 1994)" or "Malignant Neoplasm" = "Yes".

Multiple biopsies per time interval/time point: For the exit examination the last available measurement will be used if there are several measurements. For any other time intervals / time points, the analyses in which numbers of subjects are reported will be based on a 'worst case approach'. In this approach, the worst measurement within each of the above-mentioned time intervals / time points will be used. These worst outcomes across time intervals / time points are determined for each endpoint in Table 6–1.

Table 6–1: Overview of biopsy endpoints including majority result handling and worst case

Part		Endpoint	No majority available	Worst case across time intervals for subject- based analyses
		Main results		
1		Adequate endometrial tissue	- (not possible)	"Yes"
II	Main diagnosis	Benign endometrium Endometrial Hyperplasia (WHO 2014) Malignant Neoplasm	Worst case: List is ordered by severity, from low to high	List is ordered by severity, from low to high
Ш	1	Endometrial Polyp	Worst case: yes	"Yes"
IV		Tissue sufficient for PAEC read	- (not possible)	"Yes"

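### The SAP gives a majority biopsy diagnosis only when all three panel reads exist, so two concordant reads with a missing third drop out of the main endometrial evaluation

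*Protocol*

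**What the plan says.** The protocol describes two steps of central reading in 9.6.3.2.4: a safety assessment by one pathologist, then a multi-reader assessment by a panel. On coverage, section 5 speaks of "a panel of highly experienced and well renowned expert pathologists who will assess every biopsy sample taken from study participants", and 9.6.3.2.6 says that "presence of PAEC will be analyzed in all endometrial biopsy samples as part of the multi-reader assessment".

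On analysis, the multi-reader paragraph of 9.6.3.2.4 states: "The main study evaluation will be based on the majority diagnosis of the multi-reader assessment". It also says what to do when the readers disagree: "In the absence of a majority consensus, the most severe diagnosis is used". It leaves the details to pre-specified rules and does not require that all three reads exist.

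SAP 6.4.1.1 supplies those rules and begins with a condition: "Majority read results will only be provided in case biopsy data from Readers #2, #3 and #4 are available". Tissue adequacy comes next: "If at least 2 of the 3 readers consider the tissue adequate/sufficient, the majority for the main results will be assessed". If the readers who remain do not agree, Table 6-1 uses the worst case for the main results.

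The SAP plans two further displays. For the safety read, "For the safety read only one result will be available per biopsy (based on either Reader #1 or #5"). The all-reads display takes any biopsy with a result from at least one reader.

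**The concern.** The opening condition in SAP 6.4.1.1 removes a biopsy from the majority-read analysis whenever one panel read is absent, even if the other two agree. The SAP's provision for two readers does not help. It sits after the three-reader condition, so it covers a reader who reports inadequate tissue and not a read that is missing.

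Endometrial histology is a secondary safety variable, and endometrial adenocarcinoma in rodents was among the findings behind the pause. Hyperplasia and malignancy may be rare here, in which case one omitted biopsy could change the main table.

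The subject-level rule adds to this. Outside the exit examination, SAP 6.4.1.1 takes each woman's worst result within an interval. If one biopsy has two malignant reads and no third, and another in the same interval is fully read as benign, the only majority result left for her is benign.

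**Working it through.** The documents give no count or rate of incomplete panels, so there is no planned figure to reproduce. The check applies the SAP rule to every combination of reads.

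**Inputs (SAP 6.4.1.1 and Table 6-1).** Main results are ordered benign, hyperplasia, malignant. A result is given only if all three readers have data. At least two readers must find the tissue adequate. Two equal results form the majority, and otherwise the worst case is taken.

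| Two panel reads | 3rd benign | 3rd hyperplasia | 3rd malignant | 3rd inadequate | 3rd missing |
|---|---|---|---|---|---|
| benign, benign | benign | benign | benign | benign | none |
| hyperplasia, hyperplasia | hyperplasia | hyperplasia | hyperplasia | hyperplasia | none |
| malignant, malignant | malignant | malignant | malignant | malignant | none |
| benign, hyperplasia | benign | hyperplasia | malignant | hyperplasia | none |
| benign, malignant | benign | malignant | malignant | malignant | none |
| hyperplasia, malignant | malignant | hyperplasia | malignant | malignant | none |

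1. In the three concordant rows, every possible third read gives the same diagnosis. Using the two reads therefore needs no assumption about the missing one.
2. An inadequate third read and a missing third read carry the same diagnostic information, namely none. The SAP keeps the first biopsy and drops the second.
3. In the discordant rows, the SAP already takes the worst case of two reads when the third is inadequate. Doing the same for a missing read extends a rule the SAP already has, and it agrees with the protocol's most-severe rule.

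**Scale, by assumption only.** Suppose each panel read is missing independently with probability m. Then
- no majority result under the SAP: 1 − (1 − m)³
- exactly two reads: 3m(1 − m)²
- fewer than two reads: the difference between these.

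| m (assumed) | No result under SAP | Exactly two reads | Fewer than two reads |
|---|---|---|---|
| 1% | 3.0% | 2.9% | 0.03% |
| 2% | 5.9% | 5.8% | 0.1% |
| 5% | 14.3% | 13.5% | 0.7% |
| 10% | 27.1% | 24.3% | 2.8% |

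For m = 5%: 1 − 0.95³ = 0.1426 and 3 × 0.05 × 0.95² = 0.1354, leaving about 0.007. The table shows only that, if single reads go missing independently, nearly all the excluded biopsies would have two reads. It does not estimate what happened in this trial.

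**The case against.** The strongest reply is that the protocol commits the panel to read every sample, so a three-read condition excludes nothing if that commitment is kept. This is right as far as it goes. A reader might infer that the protocol and the SAP contradict each other, but they do not. The issue is only how the SAP treats a biopsy when coverage falls short. The SAP's own conditional wording, and an all-reads display that accepts a single reader, show that incomplete panels were contemplated.

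A reader might also infer that export rules will take a whole region out of the main table. The protocol sentence concerned is "If an expedited multi-reader assessment is not possible (e.g. due to sample export regulations), follow-up procedures will be decided based on the safety-reader diagnosis". It covers only the expedited read after a non-benign safety read. It names no region and does not say that the routine panel read is abandoned. Export rules would also plausibly block all three panel reads together, a case that the independence table does not describe and that a two-read rule would not restore.

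It is also tempting to say that malignancies go unreported, or that women are cleared on incomplete reads. Neither follows:
- The all-reads display counts any non-benign read. A safety read of atypical hyperplasia/EIN or malignancy is a serious adverse event (protocol 9.6.1.1), and endometrial hyperplasia is an event of special interest (9.6.1.6).
- For the individual woman, footnote 10 of the protocol calls a biopsy normal only if the safety read and all three panel reads are benign, so an incomplete panel cannot clear her.
- All safety analyses are descriptive, so no test is affected.

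One suggested safeguard is weaker than it looks. The planned analysis of single reads more severe than the majority has nothing to compare against when no majority diagnosis exists.

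**Conclusion.** The point holds for the majority-read analysis, which the protocol makes the main endometrial evaluation. There, the SAP discards biopsies whose majority is already settled and treats a missing read differently from an inadequate one, for no stated reason. This follows from the rule as written and needs no assumption about missingness.

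Its size is unknown. It is zero if every panel is complete, and the percentages above depend wholly on an assumed rate and on independence. The other displays and the event reporting limit the harm. What remains is that the main table could omit a finding that the all-reads table shows, with no planned count to explain the difference. That is worth correcting because the change is small.

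**What to change.** In SAP 6.4.1.1, replace the three-reader condition with one that derives the majority-read result whenever at least two of Readers #2 to #4 have reported. Concordant reads give the diagnosis. Discordant main results give the worst case, as Table 6-1 and the protocol's multi-reader paragraph already provide. The other no-majority entries in Table 6-1 stay as they are.

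Report by treatment group the number of biopsies with fewer than three panel reads and with fewer than two. List their available reads beside the main table.

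Do not carry the safety read into the majority table. The protocol bases the main evaluation on the multi-reader majority. It also describes the safety reader as blinded to treatment group, whereas the panel is blinded to time point as well, so mixing them would give a hybrid endpoint.

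The cost is a change of wording, some derivation code and one count table. A few results, marked by footnote, will rest on two reads. Where those two disagree, the worst case may be more severe than a full panel would have given: benign plus malignant would be recorded as malignant, although a benign third read would have made the majority benign.
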